9.5.6.2.3 Post Challenge phase (Day 2 to 8)

- Daily medical interview (including assessment of ETEC disease-specific solicited events) and focused physical examination
- Vital signs (temperature, pulse and blood pressure) will be measured at least 3 times daily

- All stools will be collected for weighing and grading. Up to 3 stool samples will be sent daily for culture. If a volunteer is unable to provide samples, they will be asked to provide a self-collected rectal swab (up to 3 per day). (If the participant does not produce a stool or enough stool on any day to obtain all samples, this will not be considered a protocol deviation.)
- Record any AEs, AESIs and SAEs
- Changes in concomitant medications will be captured
- Antibiotic treatment will be started on Day 6 (5 days after challenge) or according to criteria for early antibiotic treatment (see Section 9.4.8.2)
- Collect blood samples on Days 3, 4 and 8 for immunogenicity endpoints (exploratory)
- Collect daily fecal samples for immunogenicity endpoints (exploratory)
- Collect ETEC Impact on ADLs survey responses on Day 6

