## 2.2. Study Objectives and Endpoints

### 2.2.1. Primary Objectives and Endpoints

Primary Objective	Primary Endpoint

To evaluate the moderate and severe diarrhea attack rate after challenge with wild type enterotoxigenic E. coli (ETEC) strain E24377A

	

Moderate and severe diarrhea, as defined by <math>\geq</math> 4 grade 3-5 stools or <math>> 400</math> grams of grade 3-5 stools passed within a rolling 24-hour period, deemed attributable to ETEC.  Diarrhea episodes or ETEC symptoms beginning any time after challenge through 120 hours post-challenge may contribute toward the primary endpoint and will be followed to resolution. The end of a diarrheal episode occurs when a subject does not pass any grade 3-5 stool within 24 hours. An adjudication committee will be used to judge if the diarrhea is attributable to ETEC and determine if a participant meets the primary endpoint by considering individual data as described in the adjudication charter.  Stool grading criteria: grade 1 = firm, formed; grade 2 = soft but still formed; grade 3 = thick liquid; grade 4 = thin liquid; grade 5 = clear or translucent, watery

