## 2.5.4. Time to Event

### 2.5.4.1. Time to Primary Endpoint

The secondary clinical endpoint, time to meeting the primary endpoint, is defined as the number of hours between challenge and the first grade 3-5 stool that passes the frequency or weight threshold of moderate diarrhea, occurs within a diarrhea episode that began prior to 120 hours post challenge, and is deemed attributable to ETEC by an adjudication committee. Subjects who did not meet the primary endpoint will be censored at 120 hours post challenge.

Some subjects whose measured stools did not meet the frequency or weight thresholds for moderate or severe diarrhea may still meet the primary endpoint according to the adjudication committee. In the time to primary endpoint analysis, such subjects will be considered to have met the primary endpoint at time of antibiotic administration. As a sensitivity analysis, these subjects will be considered to have met the primary endpoint at 120 hours post challenge.

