### 2.5.4.3. Time to Diarrhea Onset

The secondary clinical endpoint, time to onset of diarrhea, is defined as the number of hours between challenge and the first grade 3-5 stool of a subject's first diarrhea episode during the inpatient period. Subjects who experienced no diarrhea episodes during the inpatient period will be censored at 120 hours post challenge.

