## 2.6. Clinical Variables

### 2.6.1. Stool Output

Every stool passed during the inpatient period (Day 1 through up to Day 9) will be collected. Clinic staff will grade each stool according to the scale in Section [2.5.1](#) Time of stool (hour and minute), stool weight (grams), and stool grade (Grade 1 through Grade 5) will be recorded and used to determine whether diarrhea occurred according to the definitions in Section [2.5.1](#).

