**RESTRICTED**

	SPONSOR: Scandinavian Biopharma Holding AM (SBH)	PROTOCOL NUMBER: OEV-131	PROTOCOL TITLE: Pre-Study of wild type Enterotoxigenic E.coli (ETEC) Strain for Verification of a planned Challenge Dose	VERSION NO: 1.0

Notes: N = Number of subjects in the Full Analysis Set.

a Time to primary endpoint is defined as the number of hours from challenge to first grade 3-5 stool that meets at least moderate severity criteria, occurs within a diarrhea episode that began prior to 120 hours post challenge, and is deemed attributable to ETEC by an adjudication committee. Subjects who met the primary endpoint according to the adjudication committee but whose stools did not meet the frequency or weight thresholds for moderate or severe diarrhea will be considered to have met the primary endpoint at time of antibiotic administration.

b Time to primary endpoint for the sensitivity analysis is defined as the number of hours from challenge to first grade 3-5 stool that meets at least moderate severity criteria, occurs within a diarrhea episode that began prior to 120 hours post challenge, and is deemed attributable to ETEC by an adjudication committee. Subjects who met the primary endpoint according to the adjudication committee but whose stools did not meet the frequency or weight thresholds for moderate or severe diarrhea will be considered to have met the primary endpoint at 120 hours post challenge.

c Time to unadjudicated primary endpoint is defined as the number of hours between challenge and the first grade 3-5 stool that passes the frequency or weight threshold of moderate diarrhea and occurs within a diarrhea episode that began prior to 120 hours post challenge.

d Time to diarrhea onset is defined as the number of hours from challenge to first grade 3-5 stool of a subject's first diarrhea episode during the inpatient period.

e Estimated time to event is based on the survival function calculated via Kaplan-Meier methodology. Subjects who did not meet the primary endpoint will be right censored at 120 hours post-challenge or time of discharge from the inpatient unit, whichever is first. Subjects who experienced no diarrhea episodes during the inpatient period will be right censored at the time of discharge from the inpatient unit.

f Confidence intervals are calculated via log-log transformation.

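### Event-free subjects are censored by 120 h but events may be timed later, so one late event takes the Kaplan-Meier curve to 100%; the onset rule also contradicts Table 15 footnote e

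*SAP*

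**What the plan says.** Table and figure numbers here are those on the SAP mock-ups; the text of SAP 5.3 cites the time-to-event table as Table 16, but the mock-up is Table 15.

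- **Event time, primary endpoint (SAP 2.5.4.1).** The time of the first loose stool that crosses the moderate threshold, provided that it "occurs within a diarrhea episode that began prior to 120 hours post challenge". The limit applies to the start of the episode, not to the stool. Section 2.5.4.2 uses the same structure for the unadjudicated endpoint.
- **Committee-added cases (SAP 2.5.4.1).** For subjects judged to meet the endpoint without crossing a stool threshold, "such subjects will be considered to have met the primary endpoint at time of antibiotic administration". A sensitivity analysis places them at 120 h instead.
- **Censoring, primary endpoint (SAP 2.5.4.1).** "Subjects who did not meet the primary endpoint will be censored at 120 hours post challenge". Table 15 footnote e says the earlier of 120 h and discharge.
- **Censoring, diarrhea onset.** SAP 2.5.4.3 counts first episodes over the whole inpatient period, yet "Subjects who experienced no diarrhea episodes during the inpatient period will be censored at 120 hours post challenge". Table 15 footnote e says "Subjects who experienced no diarrhea episodes during the inpatient period will be right censored at the time of discharge from the inpatient unit".
- **Observation after 120 h.** Episodes that start in time "may contribute toward the primary endpoint and will be followed to resolution" (SAP 2.2.1), and "Every stool passed during the inpatient period (Day 1 through up to Day 9) will be collected" (SAP 2.6.1).
- **Routine antibiotics (Protocol 9.5.6.2.3).** "Antibiotic treatment will be started on Day 6 (5 days after challenge", or sooner if the early-treatment criteria are met.
- **Output.** The PROC LIFETEST pseudocode in SAP 5.3 plots the failure curve with numbers at risk and sets no time limit.

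**The concern.** Events and censoring run on different clocks. An event may be dated after 120 h, but every event-free subject has left the risk set by then. A Kaplan-Meier step after 120 h is therefore divided only by subjects who are themselves late cases, and the last of those steps takes the survival estimate to zero.

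There are two routes to such an event for the primary endpoint: a threshold stool after 120 h in an episode that began earlier, and a committee-added case timed at Day 6 antibiotics. On the second route, the side of 120 h on which the case falls depends on the clock times of challenge and first dose.

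The text and footnote e also differ. For onset, one censors at 120 h and the other at discharge. For the primary endpoint, 2.5.4.1 would treat a subject who left at 30 h as observed event-free to 120 h, while footnote e would not. Two programmers could follow the SAP and produce different results.

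Both times are secondary endpoints (Protocol 8.2.1). Table 15 is marked for the topline report, whose results SAP 8.1 treats as final.

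**Working it through.** **1. Inputs and the plan's own figure.** SAP 2.4.1 gives 25 subjects with attack rates of 60% and 72%, that is 15 and 18 events. Exact Clopper-Pearson limits are 0.387 to 0.789 for 15/25 and 0.506 to 0.879 for 18/25. These match the SAP's (0.39, 0.79) and (0.51, 0.88). The SAP states no Kaplan-Meier figure, so the event times below are assumptions. The end value of the curve does not depend on them.

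**2. Formula.** S(t) is the product of (1 − d/r) over event times, with d events among r at risk; failure is 1 − S(t). At a tie, events precede censorings.

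**3. Rule as written, 25 subjects: 15 events before 120 h, one at 122 h, nine event-free.**
- After the early events, S = 10/25 = 0.40 (failure 60%).
- At 120 h nine subjects are censored, leaving r = 1.
- At 122 h, S = 0.40 × (1 − 1/1) = 0 (failure 100%).
- The proportion is 16/25 = 64%.

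**4. Same data, late event entered at 120 h.** Now r = 10 and S = 0.40 × (1 − 1/10) = 0.36, so failure is 64%, as in Table 12. Keeping event-free subjects at risk to about 192 h also gives 64%. Discarding the late event would end the curve at 15/25 = 60% and disagree with Table 12.

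**5. Other sizes, total events including one at 126 h.**

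| Events / N | Failure before the late event | Failure as written | Proportion |
|---|---|---|---|
| 15/25 | 56% | 100% | 60% |
| 18/25 | 68% | 100% | 72% |
| 18/30 | 57% | 100% | 60% |
| 21/30 | 67% | 100% | 70% |

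With two of the 18 events late (126 h and 130 h), the curve goes to 82% and then 100%.

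**6. Percentiles.** In every row above the 75th percentile becomes 126 h; it should be not reached. The median is unchanged in these cases with one or two late events. At 11/25 (44%), below the SAP's planning range, the median would also become 126 h instead of not reached.

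**7. The boundary.** In the 18/25 case, an event at exactly 120 h has r = 8 and gives 72%, which is correct. An event at 120.5 h gives 100%. Placing committee-added cases at 120 h, as the sensitivity analysis does, is therefore harmless.

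**8. Onset under 2.5.4.3.** Take 20 onsets by 120 h, one at 140 h and four subjects with none. Censoring at 120 h gives 80% and then 100%. Under footnote e, with those four discharged after 140 h, S = 0.20 × (1 − 1/5) = 0.16, so failure is 84% = 21/25.

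**9. How often.** The documents give no rate. Purely as assumptions, a per-subject chance of a late event of 1%, 2% or 5% gives 1 − (1 − p)^25 = 22%, 40% or 72% for at least one in 25 subjects, and 26%, 45% or 79% in 30. Protocol Table 3 reports mean times to illness of 26 to 47 h, with a range of 7 to 84 h in the one group where it is given. That suggests the low end or below.

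**The case against.** The strongest reply is that this is a conditional artefact in the tail of a secondary, descriptive output. No formal testing is planned, no decision rule uses the curves, and with no event after 120 h the curve ends correctly. The figure prints numbers at risk, so a careful reader would see a last step resting on one subject. The SAP already has a 120 h sensitivity analysis for committee-added cases, and footnote e already gives workable rules for onset and for early leavers.

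This stands and limits the importance of the point. It does not remove it. The sensitivity analysis does not help when the late event is a threshold stool. Footnote e still censors the primary endpoint no later than 120 h. The text and the footnote cannot both be programmed.

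A reader might infer more than the documents support:
- **That Listing 6 shows a late event.** Its stool at 122 h 3 min belongs to a second episode marked as not reaching the threshold, in a subject who had already qualified in the first episode (444 g at 29 h 45 min). It shows only that stools after 120 h are recorded.
- **That Table 15 would report a 100% attack rate.** It prints times only; the 100% can appear only in the figures.
- **That the Protocol's ciprofloxacin side-effect rate gives the chance of a late event.** That rate pools nausea, vomiting and diarrhea. New diarrhea after antibiotics could bear on onset but not on the primary endpoint, whose episodes must begin before 120 h.

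**Conclusion.** The rules are wrong as written and should be fixed before topline programming. If at least one event is dated after 120 h, the primary-endpoint curve in Figure 2 ends at 100% instead of the crude proportion (100% against 64% in the 16/25 example). The unadjudicated curve, and Figure 3, do the same when the late event is a threshold stool. In Table 15 the 75th percentile becomes the late event time instead of not reached. In the cases computed at the SAP's 60% and 72% rates, the median is unaffected.

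Diarrhea onset has the same flaw under 2.5.4.3 but not under footnote e; the problem there is the contradiction between them. Section 2.5.4.1 and footnote e also disagree for subjects who leave before 120 h.

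The arithmetic is certain once a late event occurs; whether one will is unknown and probably uncommon. A reader might infer that the main result is at risk. It is not: the primary proportion and its Clopper-Pearson interval in Table 12 do not use these times.

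**What to change.** State one rule, in the same words, in SAP 2.5.4.1 to 2.5.4.3 and Table 15 footnote e.

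1. **Primary and unadjudicated endpoints, events.** Enter any event time after 120 h at 120 h for the Kaplan-Meier analysis, including committee-added cases timed at antibiotic administration. Keep the true time in the listing.
2. **Primary and unadjudicated endpoints, censoring.** Censor event-free subjects at the earlier of 120 h or the end of inpatient observation.
3. **Diarrhea onset.** Keep the inpatient-period definition and censor at discharge, as footnote e says. Onset should not be restricted to episodes starting by 120 h, because Protocol 8.2.1 sets no such limit.
4. **Programming check.** When nobody leaves before 120 h, the final Kaplan-Meier incidence must equal the Table 12 proportion for each of the two endpoints.

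The cost is SAP wording, a small change to the derivation of event and censoring times, and the check. No new data are needed and no protocol endpoint changes.

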8.1.1 Primary endpoint

Moderate and severe diarrhea, as defined by ≥ 4 grade 3-5 stools **or** > 400 grams of grade 3-5 stools passed within a rolling 24-hour period, deemed attributable to ETEC.

Diarrhea episodes or ETEC symptoms beginning any time after challenge through 120 hours post-challenge may contribute toward the primary endpoint and will be followed to resolution. The end of a diarrheal episode occurs when a subject does not pass any grade 3-5 stool within 24 hours. An adjudication committee will be used to judge if the diarrhea is attributable to ETEC and determine if a subject meets the primary endpoint by considering individual data as described in the adjudication charter.

Stool grading criteria: grade 1 = firm, formed; grade 2 = soft but still formed; grade 3 = thick liquid; grade 4 = thin liquid; grade 5 = clear or translucent, watery

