9.7.2 Analysis of Clinical and Microbiology endpoints

For the primary endpoint, the proportion of subjects with moderate and severe diarrhea (defined as ≥ 4 grade 3-5 stools **or** > 400 grams of grade 3-5 stools passed in a rolling 24-hour period), deemed attributable to ETEC by an adjudication committee, will be presented with point estimate and the corresponding two-sided 95% confidence interval. For secondary clinical and microbiology endpoints, descriptive statistics will be presented, including two-sided 95% confidence intervals where applicable. For time to event analysis (time to onset of diarrhea and time to primary endpoint) Kaplan-Meier time to event methods will be used.

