## 2.5.3. Unadjudicated Primary Endpoint

The unadjudicated primary endpoint, defined only by objective stool output criteria without adjudicator input, will be assessed as a sensitivity analysis. The unadjudicated primary endpoint is defined as  $\geq 4$  grade 3-5 stools or  $> 400$  grams of grade 3-5 stools passed within a rolling 24-hour period. Diarrhea episodes beginning any time after challenge through 120 hours post-challenge may contribute toward the unadjudicated primary endpoint.

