## 16.2.6 Individual Clinical Data

### 16.2.6.1 Grade 3-5 Stool Output

#### Listing 6: Grade 3-5 Stool Output\*

[Implementation Note: The text in blue shows an example entry. Actual data should be presented in black text.]

Subject ID	Diarrhea Episode a No.	Grade 3-5 Stool No.	Time of Grade 3-5 Stool Relative to Challenge	Stool Weight	Stool Grade	Grade 3-5 Stools Passed within Previous 24 Hours	Total Number of Grade 3-5 Stools within Previous 24 Hours	Total Weight of Grade 3-5 Stools within Previous 24 Hours	Did Episode Meet Frequency and/or Weight Threshold for Primary Endpoint?	Did Episode Begin Prior to 120 Hours Post Challenge?	Did Subject Meet Unadjudicated Primary Endpoint? b	Did Subject Meet Primary Endpoint? c	Qualifying Information Provided by Adjudication Committee
xxxx	1	1	13 hrs, 2 min	105 g	5	Stool 1	1	105 g	Yes	Yes	Yes	Yes	-
		2	16 hrs, 14 min	232 g	5	Stools 1-2	2	337 g					
		3	29 hrs, 45 min	107 g	3	Stools 1-3	3	444 g					
		4	42 hrs, 29 min	52 g	2	Stools 3-4	2	159 g					
	2	1	105 hrs, 55 min	32 g	3	Stool 1	1	32 g	No	Yes	Yes	Yes	-
		2	122 hrs, 3 min	30 g	3	Stools 1-2	2	62 g					

Notes: Yellow highlighted cells indicate that the stool frequency or weight threshold for the primary endpoint has been met.

a A diarrhea episode starts when the first grade 3-5 stool that contributes to diarrhea of any severity is passed. A diarrhea episode ends when a subject has not passed any grade 3-5 stools within the past 24 hours.

b Moderate to severe diarrhea is defined as having a moderate and/or severe diarrhea episode beginning prior to 120 hours after challenge.

c The primary endpoint is defined as having a moderate and/or severe diarrhea episode or ETEC symptoms beginning prior to 120 hours after challenge, deemed attributable to ETEC as decided by an adjudication committee of experts in diarrheal illness.

RESTRICTED

DOCUMENT REF.: SOP-ST-01  
LAST REVISION DATE: N/A  
VERSION NO.: 1.0

DOCUMENT NAME:  

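### No planned table gives the proportion that Protocol 9.7.2 describes: the SAP's committee row can include below-threshold subjects, and its stool-output row drops attribution to ETEC

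*SAP*

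**What the plan says.** **Text that requires the threshold.** Protocol 8.1.1 opens with the definition: "Moderate and severe diarrhea, as defined by ≥ 4 grade 3-5 stools", or more than "400 grams of grade 3-5 stools passed within a rolling 24-hour period, deemed attributable to ETEC". Protocol 9.7.2 repeats the threshold for the primary analysis and describes the proportion as "deemed attributable to ETEC by an adjudication committee, will be presented with point estimate". Protocol 8.2.1 times the endpoint at the stool that reaches the moderate criterion, so it assumes that every case has such a stool. SAP 2.2.1 carries the 8.1.1 text over.

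**Text that leaves room.** Protocol 8.1.1 goes on: "Diarrhea episodes or ETEC symptoms beginning any time after challenge through 120 hours post-challenge may contribute toward the primary endpoint". It then says: "An adjudication committee will be used to judge if the diarrhea is attributable to ETEC and determine if a subject meets the primary endpoint". The details are left to an adjudication charter. The synopsis has the same sentences, and Protocol 9.8 repeats the committee's role.

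**What the SAP does with it.** SAP 2.5.2 makes the determination a majority vote under the charter. SAP 2.5.4.1 then states: "Some subjects whose measured stools did not meet the frequency or weight thresholds for moderate or severe diarrhea may still meet the primary endpoint". Such subjects get the time of antibiotic administration as their event time, or 120 hours in a sensitivity analysis, and the notes to Table 15 repeat this. Note c of Listing 6 reads: "The primary endpoint is defined as having a moderate and/or severe diarrhea episode or ETEC symptoms beginning prior to 120 hours after challenge", subject to the committee's attribution. SAP 2.5.3 adds: "The unadjudicated primary endpoint, defined only by objective stool output criteria without adjudicator input, will be assessed as a sensitivity analysis". SAP 5.1 and the Table 12 mock-up report the committee result and this stool-output result, and no other version.

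**The concern.** The primary objective is one number, the attack rate of moderate and severe diarrhea at this challenge dose, and it is wanted for planning a phase 3 challenge study. With 25 to 30 subjects, who counts in the numerator matters. The rule that allows below-threshold subjects to count sits in a time-to-event subsection, and the SAP gives no criteria for using it.

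The protocol already has a separate name for a wider outcome. The notes to its Tables 2 and 3 describe moderate to severe ETEC illness as including mild diarrhea with moderate to severe gastrointestinal symptoms. Counting below-threshold subjects on the strength of symptoms would move the reported diarrhea rate toward that outcome while keeping the diarrhea label.

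The situation can arise. Under Protocol 9.4.8.2 and SAP 2.6.4, early antibiotics may start for diarrhea of any severity with two or more listed symptoms, so treatment can come before the threshold is reached. The SAP's use of antibiotic time as the event time fits that picture.

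**Working it through.** **Inputs.** N is 25 to 30 (Protocol 9 and 9.3.4). The planning rates are 60% and 72% of 25 with Clopper-Pearson 95% intervals (SAP 2.4.1). The two reported rows come from SAP Table 12. The number of below-threshold cases is not in the documents, so I take 0 to 3 as an assumption.

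**1. Reproduce the SAP's intervals.** For x events in n, the lower limit is the 0.025 quantile of Beta(x, n−x+1) and the upper limit is the 0.975 quantile of Beta(x+1, n−x).
- 15/25: (0.387, 0.789). The SAP has (0.39, 0.79).
- 18/25: (0.506, 0.879). The SAP has (0.51, 0.88).

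Both agree.

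**2. What each row counts.** Let A be subjects who met the threshold with diarrhea judged attributable, D those who met the threshold but were judged not attributable, and U those below the threshold whom the committee still counts.
- Committee row: (A + U)/N
- Stool-output row: (A + D)/N
- Protocol 9.7.2: A/N

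The difference between the two rows gives only U − D. A cannot be recovered from them unless U or D is known.

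**3. The rows can agree and still both differ from the protocol quantity.** Take A = 15, U = 3, D = 3, N = 25. Both rows read 18/25 = 72%, while A/N = 15/25 = 60%. Agreement between the rows is therefore not evidence that no one was reclassified.

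**4. Size of the upward part alone (D = 0).** One case is worth 1/25 = 4.0 points or 1/30 = 3.3 points.

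| Below-threshold cases (assumed) | Starting from 15/25 | Starting from 18/30 |
|---|---|---|
| 0 | 60% (38.7 to 78.9) | 60% (40.6 to 77.3) |
| 1 | 64% (42.5 to 82.0) | 63.3% (43.9 to 80.1) |
| 2 | 68% (46.5 to 85.1) | 66.7% (47.2 to 82.7) |
| 3 | 72% (50.6 to 87.9) | 70.0% (50.6 to 85.3) |

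At n = 25, three cases span the gap between the SAP's two planning rates. That is a yardstick, not a forecast.

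**5. What can be derived.** Listing 6 shows, per subject, whether the stool-output endpoint was met and whether the committee's endpoint was met. Counting subjects with yes to both gives A. A subject counted on symptoms with no grade 3-5 stool might not appear in that listing, but would belong to U and not to A. No count from the listing is planned.

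**The case against.** The strongest reply is that the protocol supplies the latitude. Its synopsis and 8.1.1 let symptoms contribute and have the committee determine the endpoint, not only attribution. On that reading, note c of Listing 6 repeats the protocol, and the criteria for counting a below-threshold subject belong in the charter, which was to be fixed before the in-patient period and may be narrow. This stands in part. A reader might infer that the SAP replaced a clear protocol endpoint, and the documents do not support that. It still leaves 9.7.2, 8.2.1 and the opening of 8.1.1 unreconciled with SAP 2.5.4.1.

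Four other tempting readings go too far:
- **The reported rate will be inflated.** The committee can also remove threshold cases, so the net direction is unknown, and it may add no one.
- **These subjects never reached the threshold.** The SAP speaks of measured stools, which could cover lost or unweighed output.
- **Earlier studies show that such cases are common.** Protocol Table 3 gives early antibiotics in 12/15 and 8/16 subjects. The 15 equals the number with moderate or severe illness in that study, out of 20 challenged, and the early-treatment criteria include outputs above the threshold. These figures say little about below-threshold illness.
- **Phase 3 will be undersized.** The phase 3 endpoint is not given. If it uses the same adjudication, the committee rate is the relevant planning figure.

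It is also fair that the rule is disclosed, that the stool-output rate stands beside the committee rate in the topline results, and that no hypothesis is tested. None of this supplies the missing proportion.

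**Conclusion.** The point holds as a gap in reporting and a conflict in wording; it should be fixed, but it does not invalidate the study. The SAP allows below-threshold subjects to count as primary cases, and neither row of Table 12 is the threshold-and-attributable proportion that Protocol 9.7.2 describes.

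The possible size is 4.0 points per such subject at n = 25 and 3.3 at n = 30. For an assumed 0 to 3 such subjects, a 60% rate at n = 25 would read between 60% and 72%. Zero is as consistent with the documents as three, and cases the committee removes work in the other direction. The conclusion rests on reading 9.7.2 as the definition of the primary analysis and on a charter that could not be checked.

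**What to change.** 1. In SAP 2.5.2 and Table 12, report as the estimate matching Protocol 9.7.2: threshold met in an episode starting by 120 hours, and a majority vote that the diarrhea is attributable to ETEC.
2. Show the wider committee result in its own labelled row. Beside it, give the numbers reclassified up and down, and how many of those reclassified up had antibiotics before reaching any threshold. Keep the stool-output row.
3. In SAP 2.5.4.1 and the Table 15 notes, tie the antibiotic-time imputation, and its 120-hour alternative, to the wider result only.
4. Reconcile the symptom wording together in the protocol synopsis, Protocol 8.1.1, SAP 2.2.1, Listing 6 note c and the charter. Editing note c alone would leave it out of line with the others.

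The cost is one extra table row, some counts from data already listed, and aligned wording. The drawback is that the threshold-based rate may be lower if antibiotics cut illness short before the threshold. The wider row and the antibiotic count in item 2 let a reader see how far that applies.
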